### **Optional Correlative Sample Collection**

Blood sample collection, for the assessment of lung, muscle, and brain injury biomarkers, and other future research studies will occur at the time points indicated in the Study Schema for patients that have provided informed consent on the optional consent for blood sample collection. It is not mandatory for all sites to participate in the collection of correlative samples and each site's willingness and ability to participate will be discussed on a case-by-case basis. Further details are available in the Manual of Procedures.

---

## TRIAL INTERVENTIONS

### Early Cohort

#### Intervention Arm:

[figure not shown]
Patients randomized to receive corticosteroids will receive dexamethasone 20mg daily for 5 days and then 10mg for an additional 5 days, for a total of 10 days or until ICU discharge or death, whichever comes first. After 10 days dexamethasone will be stopped without a taper. If a patient is discharged from the ICU prior to completing the protocol, then ongoing corticosteroid management will be up to the treating team as per SOC.

Dexamethasone will be administered parenterally (intravenous administration). Specific details on the timing of administration are provided below;

- 20mg dexamethasone is to be administered as soon as possible and on the day of randomization (Day 0), and this dose will be administered daily for a total of 5 days of treatment (Day 0 – Day 4). Then, the dexamethasone dose will be reduced to 10mg and this dose will be administered daily for a total of 5 days (Day 5 – Day 9).
- In rare cases where it is not possible to administer the first dose of study drug on the same day as randomization (e.g., if the patient is randomized very close to midnight), 20 mg dexamethasone can be started the day following randomization (Day 1), and will be administered daily for a total of 5 days of treatment (Day 1 – Day 5). Then, the dexamethasone dose will be reduced to 10mg and this dose will be administered daily for a total of 5 days (Day 6 – Day 10).

Patients finishing 10 days of dexamethasone as part of the Early Cohort will be eligible for randomization in the Extended Cohort if they are still requiring HFNC, NIV, IMV or ECLS, and according to the other eligibility criteria for the Extended Cohort.

**Control Arm:** Those randomized to usual care will receive routine AHRF management without corticosteroids. All other aspects of care will be at the discretion of the treating team including antibiotics, intravenous fluids, mechanical ventilation and ECLS.

**Early Cohort Study Treatment Schedule Tables:**

Early Cohort – Intervention Arm Patients			Early Cohort – Control Arm Patients	
Treatment	Day 0 (Early Cohort Randomization) to Day 4*	Days 5 to 9*	Treatment	Day 0 (Early Cohort Randomization) to Day 9
20 mg Dexamethasone	X		Routine AHRF management without corticosteroids	X
10 mg Dexamethasone		X		

[figure not shown]
*\*The Day numbers may be shifted back by 1 day for patients that are not able to receive their first dose of study drug on the same day as randomization (per the section above).*

**Extended Cohort**

**Intervention Arm:** Patients randomized to receive extended dexamethasone will receive dexamethasone 10mg for an additional 10 days. At the end of the additional 10 days, the dexamethasone dose will be halved to 5mg for another 5 days (to reduce the risk of adrenal insufficiency) and then stopped (including taper, a total of 23-27 days (depending on the length of their initial course of dexamethasone [8-12 days]) or until ICU discharge or death, whichever comes first). A taper is encouraged, however not mandated even if the patient is sent to the ward. If a patient is discharged from the ICU prior to completing the protocol, then ongoing corticosteroid management will be up to the treating team as per SOC.

Dexamethasone will be administered parenterally (intravenous administration). Specific details on the timing of administration are provided below;

- Dexamethasone is to be administered such that there is no lapse in dexamethasone treatment (no dexamethasone free day in between their last dose from Early Cohort or SOC and their first day of dexamethasone treatment as part of the Extended Cohort).
- If the patient is randomized the day after they received their last dexamethasone dose as part of the Early Cohort or SOC; 10mg dexamethasone will be administered on the day of randomization (Day 0) and this dose will be administered daily for a total of 10 days of treatment (Day 0 – Day 9). Then, the dexamethasone dose will be reduced to 5mg and this dose will be administered daily for a total of 5 days (Day 10 – Day 14).
- If the patient is randomized on the same day they are receiving their last dexamethasone dose as part of the Early Cohort or SOC; 10mg dexamethasone will be administered on the next day (Day 1) and this dose will be administered daily for a total of 10 days of treatment (Day 1 – Day 10). Then, the dexamethasone dose will be reduced to 5mg and this dose will be administered daily for a total of 5 days (Day 11 – Day 15).

**Control Arm:** Those randomized to the comparator arm will stop corticosteroids after their initial course without a taper. All other aspects of care will be directed by the treating team.

**Extended Cohort Study Treatment Schedule Tables:**

Extended Cohort – Intervention Arm Patients			Extended Cohort – Control Arm Patients	
Treatment	Day 0 (Extended Cohort Randomization) to Day 9*	Days 10 to 14*	Treatment	Day 0 (Extended Cohort Randomization) to Day 14
10 mg Dexamethasone	X		Routine AHRF management without corticosteroids	X
5 mg Dexamethasone		X		

*\*The Day numbers may be shifted back by 1 day for patients that are not able to receive their first dose of study drug on the same day as randomisation (per the section above).*

**Characterization and Accountability of Study Drug**

Dexamethasone is an approved corticosteroid that is routinely stocked and used in hospital settings; it will be provided from the local site supply. Sites will be responsible for assuring adequate local supply, accountability and destruction in coordination with local pharmacy practice and any applicable regulations.

[figure not shown]
In jurisdictions where it is labeled as an investigational medicinal product for the purpose of this study, it should not be used for any purpose outside the scope of this protocol, nor can it be transferred or licensed to any party not participating in the study.

For more information, please refer to the study pharmacy manual (if applicable).

**Participant Compliance and Dropout**

We do not expect issues with protocol adherence as corticosteroids are commonly used, and all study drugs will be administered by ICU nurses. We will capture open label corticosteroid use in those randomized to SOC in the Early Cohort, and extended corticosteroid use in those randomized to stop corticosteroids at 10 days in the Extended Cohort but we expect the number of crossovers to be small.

---

---

### **Premature Withdrawal/Discontinuation Criteria**

Treating physicians may choose to discontinue therapy at their discretion, including any situation that occurs such that continued participation in the study would not be in the best interest of the participant.

Participants are free to withdraw from participation in the study at any time upon request. Discontinuation of the study drug regardless of the reason (e.g. patient or physician request, or adverse event), does not constitute study withdrawal. Patient follow-up data will still be collected as planned and analyzed as intent to treat unless the participant withdraws consent for continued follow-up.

Patients that are withdrawn at any time after randomization will not be replaced.

[figure not shown]
### **CONCOMITANT MEDICATION/PROCEDURES**

The administration of the following concomitant medications will be collected for study purposes from time of consent to time of ICU discharge or for 30 days, whichever is shorter.

- Antivirals (e.g., Remdesivir; COVID specific medications)
- Interleukin (IL)-6 Inhibitors
- Janus Kinase (JAK) Inhibitors
- Neuromuscular blocking agents (e.g., Rocuronium, Cisatracurium)
- Sedatives and Opioids (e.g., Propofol, Midazolam, Fentanyl, Ketamine, Hydromorphone)
  - Inotropes (e.g., Dobutamine, Milrinone)
- Vasopressors (e.g., Norepinephrine, Vasopressin, Epinephrine)

Additionally, the following procedures are to be documented:

- ECMO
- Prone positioning
- Renal replacement therapy

## SAFETY AND REPORTING REQUIREMENTS

Critically ill patients are admitted to the ICU for life-sustaining therapies (e.g. mechanical ventilation, vasopressors, renal replacement therapy). Many of the potential participants will be admitted with the expectation of receiving end-of-life care and possibly dying in the ICU. Furthermore, medical complications are likely to occur in this population, consistent with the nature of their severe illness (e.g., nosocomial infections; septic shock; multi-organ failure; need for vasopressors; acute renal failure and need for renal replacement therapy; arrhythmias; cardiac arrest; coma; aspiration; venous thromboembolism). Due to these relatively unique morbidity and mortality expectations in the critically ill patient population and the intervention's safety profile, generic adverse events will not be collected for this study and only studyprocedure related SAEs will be collected and reported (see section below). Expected events occurring in the course of critical illness, and not related to the study drug, will not be reported as SAEs in the CORT-E2 trial.

[figure not shown]
### Serious Adverse Event

A serious adverse event (SAE) in the CORT-E2 trial is defined as:

- a) any event that is fatal or immediately life threatening, permanently disabling, severely incapacitating, or requires prolonged inpatient hospitalization,
- OR...**
- b) any event that may jeopardize the patient and requires medical or surgical intervention to prevent one of the outcomes listed above,
- AND...**
- c) which the attending physician believes to be **related\*** to the study drug

*\*A related event is an event in which there is a reasonable possibility that the study procedure caused or contributed (definitely, probably, or possibly) to the SAE; this conclusion may be supported by the following observations, though these are not required for the determination of relatedness:*

- *There is a plausible time sequence between study drug administration and onset of the SAE;*
- *There is a plausible biological mechanism through which study drug may have caused or contributed to the SAE;*

---

---

## Reporting Serious Adverse Events

All SAEs as defined above must be recorded on case report forms. In addition, they must be reported using the SAE form and submitted to Ozmosis within 24 hours of becoming aware of the event.

**All** reportable SAEs must be reported as follows:

Within 24 hours: Report initial information (on trial specific SAE report form) by email to:

Ozmosis Research Inc.  
[contact]  
E-mail: [contact]

The initial information should always include:

- Name of Reporter/Investigator
- Participant Identification -
- Adverse Event Term

[figure not shown]
Within 3 calendar days: E-mail completed trial-specific SAE form including:

- Any information required per the SAE report form that was not included in the initial report
- Any additional, relevant and **de-identified** clinical notes, diagnostic test results and medical interventions
- Ensure that the patient eCRF pages are complete

## Procedure for Expedited Reporting

### Responsibility for Reporting SAEs to Health Canada

Ozmosis Research Inc. will provide expedited reports of SAEs to Health Canada according to applicable guidelines and regulations (including the 7-day notification for death and lifethreatening events), i.e. events which are BOTH serious AND unexpected, AND which are thought to be related to protocol treatment (or for which a causal relationship with protocol treatment can not be ruled out).

#### Responsibility for Reporting SAEs to Sponsor

Ozmosis will be responsible for submitting SAE reports (Initial and/or Follow-up reports) received from the sites, to the Sponsor and the domain Principal Investigators within 1 business day after receipt of the SAE form at Ozmosis.

#### Reporting SAEs to the Data Safety Monitoring Board (DSMB)

Ozmosis will be responsible for submitting SAE reports received from the sites to the DSMB chair. The SAE reports will be sent along with a synthesis from Sponsor and Domain Lead Investigators.

#### Reporting Serious Adverse Events to Local Research Ethics Boards

Investigators must follow their local Research Ethics Boards (REBs)/Institutional Review Boards (IRBs) guidelines for SAE reporting. Documentation of correspondence with REBs/IRBs should be forwarded to Ozmosis.

Documentation can be any of the following:

- letter from the REB/IRB acknowledging receipt
- stamp from the REB/IRB, signed and dated by REB/IRB chair, acknowledging receipt
- letter stating the SAE was sent to the board

#### **Reporting & Follow Up of Serious Adverse Events**

[figure not shown]
All SAEs (as defined above) occurring from the time of randomization to time of ICU discharge or 30 days (whichever is shorter) must be reported to Ozmosis.

The investigator shall provide follow-up information as and when available in a new follow-up SAE form. All SAEs must be followed until resolved, become chronic, or stable unless the participant is lost to follow up. Resolution status of such each SAE must be documented in the eCRF.

#### **STATISTICAL ANALYSES**

##### **Study Population**

We plan to recruit approximately 2 patients per site per month per domain. Given how ubiquitous AHRF is (30-50 admissions per site per month), this is a very conservative estimation of potentially eligible patients. With 30-40 sites, this will translate into approximately 70-90 patients enrolled per month and 800-1000 per year. We plan to recruit for 2.5 years to allow for a rolling start given

that sites will be initiating recruitment in a staggered fashion due to anticipated delays in ethics and contract approval, exacerbated by delays associated with COVID.

### Sample Size

The Bayesian approach does not require a fixed sample size as the trial will continue enrolling until any of the following statistical triggers are met:

- A. Superiority ( $\geq 99\%$  posterior probability of  $OR < 1$  for 60-day mortality) or
- B. Inferiority ( $\geq 99\%$  posterior probability of  $OR > 1$  for 60-day mortality) or
- C. Equivalence ( $\geq 90\%$  posterior probability of  $0.8 < OR < 1.2$  for 60-day mortality).

[figure not shown]
These triggers will be evaluated separately in Early Cohort and Extended Cohort with decisions for stopping made separately in each Cohort. To estimate potential sample size requirements, ensure adequate statistical power and compute the risk of incorrectly concluding superiority in the absence of any benefit (Type I error), we conducted statistical simulations for a range of plausible scenarios for treatment effects ( $OR = 0.75, 0.8, 0.9, 1.0$ ). These scenarios were based on our previous meta-analysis that demonstrated an  $OR$  of  $0.73-0.79$  for corticosteroids in reducing mortality in COVID or non-COVID AHRF, depending on baseline risk, estimated from a large Toronto registry (<https://criticalcare.utoronto.ca/icore>). We adjusted for differences in baseline risk using Bayesian logistic regression. Our simulations suggest a maximum expected sample size of approximately 2000 patients for each of Early Cohort and Extended Cohort (simulations were extremely similar for both domains) would be suitable. This provides a power of 94% for an  $OR$  of 0.75, the most plausible  $OR$  given the previous meta-analysis, 0% probability of concluding inferiority when  $OR > 1$  and a Type I error under the null scenario ( $OR = 1.0$ ) of below 5% at any time during enrolment.

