
Domain Secondary Outcome:
	
 
1. Mortality at other endpoints (ICU/hospital discharge, 30 days and 6 months)
 
2. Hospital length of stay
 
3. Duration of NIV
 
4. Duration of supplemental oxygen use
 
5. Ordinal scale of daily respiratory support
 
6. Need for ECLS
 
7. Duration of ECLS (for those that require ECLS)
 
8. Ventilator-free days (VFDs) censored at day 30
 
9. Health-related quality of life at 6 months (measured with EQ-5D)
 
10. Complications from Corticosteroids: 
 
a. Hyponatremia (serum sodium > 150 mmol/L)
 
b. Hyperglycemia (requiring new insulin or increase in insulin by >30% from initial/baseline dose)
 
c. Delirium
 
d. Clinically important GI bleeding (requiring endoscopy or RBC transfusion)
 
e. Nosocomial infection
 
f. Neuromuscular weakness
 
 
 

Domain Design:
	
A phase III, interventional, open-label, randomized, multi-site study

Duration:
	
2.5 years of accrual and 6 months follow-up for a total study duration of approximately 3 years.

Planned Total Sample Size:
	
The Bayesian approach does not require a fixed sample size as the trial will continue enrolling until a statistical trigger is met (see section Sample Size for additional details). It is estimated that a maximum of 2000 patients will be enrolled in each cohort at 30 to 40 sites.

Inclusion/Exclusion Criteria:	
Patients will be eligible for enrolment in this domain if they meet the PRACTICAL platform eligibility criteria and the criteria specific to either cohort in the CORT-E domain.
 
PRACTICAL Inclusion Criteria
 
1) Acute hypoxemic respiratory failure meeting all of the following criteria;
 

a) New or worsening respiratory symptoms developing within 2 weeks prior to the onset of need for oxygen or respiratory support

b) Receiving any of the following types of oxygen or respiratory support for at least 4 hours prior to the time of randomization; supplemental oxygen at 10 L/min or higher, high flow nasal oxygen (at any flow rate),

--------------------------------------	--

[figure not shown]

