### **Analyses**

Any deviation from the original statistical plan will be described in the final report.

[figure not shown]

All analyses, interim and final, will use the intention-to-treat principle. The baseline characteristics comparing randomized groups will be reported using means (and standard deviations), medians (and interquartile ranges) or proportions. Trial data will be analyzed using Bayesian hierarchical generalized linear models to estimate the posterior probability of superiority (or inferiority) and equivalence for each intervention within each domain. The hierarchical model will account for centre, time period, sex and oxygen support at the time of randomization (HNFC, NIV, invasive mechanical ventilation or ECLS). Posterior probability distributions will be computed by combining the likelihood function with minimally informative priors and updated every three months as information (observations) accumulate in the trial. Statistical analysis will be adjusted for whether a patient was enrolled in one CORT-E cohort or both CORT-E cohorts. We do not expect interaction between CORT-E and the other PRACTICAL domains. The final study analysis, separate for each cohort, will be completed once either superiority, inferiority or equivalence has been observed and confirmed by the DSMB and Platform Steering Committee.

We will collect sex and perform subgroup analysis based on this variable. It is less feasible to collect gender as most patients will not be conscious at the time of enrolment. We don't expect effect modification for either cohort based on sex or gender. Understanding the CORT-E eligibility criteria, we plan to enroll a diverse population of patients representative of the demographics of ICU patients presenting at the participating sites.

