As above, in keeping with the Bayesian framework, frequent reassessments of posterior distribution will occur. We plan to perform these analyses after each 200 patients have been randomized (after we have primary outcome data for each 200 patients). We will not start these interim analyses until at least 750 patients have been enrolled (again, until we have outcome data for at least 750 patients) in each domain in order to decrease the likelihood of spurious early findings based on an insufficient number of observations. These analyses will remain blinded to all study investigators and will be reviewed only by the DSMB. If stopping criteria are met, the DSMB may suggest stopping enrolment to one or both cohorts. The stopping criteria are intentionally conservative to avoid inappropriately stopping the trial early.

Six subgroups apply to both cohorts: 1) patients < 65 versus  $\geq$  65 years (hypothesizing that younger patients will benefit more from early and extended corticosteroids); 2) patients requiring HFNC or NIV versus invasive mechanical ventilation at the time of randomization (hypothesizing that patients receiving invasive ventilation will benefit more from early and extended corticosteroids); 3) male vs. female sex (hypothesizing no difference); 4) those requiring ECLS at baseline versus not requiring ECLS (hypothesizing that those requiring ECLS will benefit more

from early and extended corticosteroids; and 5) patients requiring versus not requiring vasopressor support at randomization (hypothesizing that those requiring vasopressor support will benefit more from early and extended corticosteroids). Two subgroups will apply exclusively to Extended Cohort 1) patients with COVID versus those with non-COVID AHRF (hypothesizing that those with COVID will benefit more from extended corticosteroids), 2) patients enrolled only in Extended Cohort versus those enrolled in both Early Cohort and Extended Cohort (to assess for interaction between cohorts). We will collect plasma samples at baseline to allow for post-hoc subgroup analysis for Early Cohort and Extended Cohort based on inflammatory groups (hypothesizing that those with elevated inflammatory markers [IL-6, sTNFr1 and IL-8] will benefit more from corticosteroids). We will perform these subgroup analyses only for the primary outcome.

[figure not shown]

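### Under the stated triggers and looks, 94% power at an odds ratio of 0.75 and a maximum of 2000 patients per cohort cannot both hold

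*Protocol*

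**What the plan says.** The Sample Size section makes enrolment open-ended: it continues until one of three triggers is met, judged separately in each cohort. The triggers are 99% posterior probability of benefit, 99% of harm, or 90% that the OR lies between 0.8 and 1.2. It then states: "Our simulations suggest a maximum expected sample size of approximately 2000 patients for each of Early Cohort and Extended Cohort". The next sentence attaches power and a type I error below 5% to that size: "This provides a power of 94% for an" OR of 0.75.

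The synopsis repeats the open-ended rule and adds: "It is estimated that a maximum of 2000 patients will be enrolled in each cohort at 30 to 40 sites".

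The Analyses section ties the end of each cohort to a trigger: "The final study analysis, separate for each cohort, will be completed once either superiority, inferiority or equivalence has been observed". It sets a first interim look at 750 patients with outcome data and then says: "We plan to perform these analyses after each 200 patients have been randomized". Earlier in the same section the posterior is to be "updated every three months as information (observations) accumulate in the trial".

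The control mortality used in the simulations is not given. The Background puts mortality at 20% to 50%. The Study Population section plans 800–1000 patients a year for 2.5 years.

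**The concern.** The number 2000 carries two meanings. An expected size is an average over simulated trials, and a sizeable share of trials exceed it. A maximum is a limit that none exceeds. A design that stops only on a trigger has a long right tail in sample size, and the trials in that tail contribute to its power. Cutting the tail off at the average removes that part of the power.

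The sponsor, the funder and the data safety monitoring board (DSMB) all read power and size together. If 2000 is the limit, power for the effect called most plausible is overstated. If 94% is to hold, the number of patients and the accrual period that may be needed are understated. The choice also decides whether a cohort can end without any of the three conclusions, a case for which the Analyses section has no rule.

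**Working it through.** **Inputs from the protocol.** Triggers: Sample Size section. Looks at 750, 950, 1150 and so on: Analyses section. Allocation 1:1: Randomization Scheme. Minimally informative prior: Analyses section, taken here as flat on the log OR. **Assumption:** control mortality of 20–50%, the Background range, because the simulated value is not stated.

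**Method.** At each look the posterior of the log OR is approximated as normal, with mean θ (the observed log OR) and variance SE² = the sum of the reciprocals of the four cell counts.
- Superiority: Φ(−θ/SE) ≥ 0.99, that is θ/SE ≤ −2.326. Inferiority is the mirror image.
- Equivalence: Φ((ln 1.2 − θ)/SE) − Φ((ln 0.8 − θ)/SE) ≥ 0.90.

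Binomial outcomes were simulated, 40,000 trials per cell, (a) until a trigger was met and (b) with a last look at 2000.

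| Control mortality | (a) Power, OR 0.75 | (a) Type I error, OR 1.0 | (a) Largest mean N, OR 0.75–1.0 | (b) Power, OR 0.75 | (b) No trigger by 2000, OR 0.75 |
|---|---|---|---|---|---|
| 20% | 93.5% | 4.5% | 2490 | 64% | 33% |
| 25% | 93.7% | 4.1% | 2170 | 71% | 25% |
| 30% | 93.7% | 3.9% | 1960 | 77% | 18% |
| 34% | 93.7% | 4.0% | 1860 | 80% | 15% |
| 40% | 93.7% | 3.5% | 1740 | 83% | 12% |
| 50% | 93.9% | 3.6% | 1670 | 86% | 9% |

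**The plan's own figures.** Run (a) reproduces 94% and the type I error below 5% at every control mortality. At about 30% mortality its largest average size is also close to 2000. Run (b) does not reach 94% anywhere in the range.

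**Hand check, one look at 2000, control mortality 34%.** Treated odds are (0.34/0.66) × 0.75 = 0.386, a risk of 0.279. SE = √[1/(1000 × 0.34 × 0.66) + 1/(1000 × 0.279 × 0.721)] = 0.0971. Then |ln 0.75|/SE = 0.2877/0.0971 = 2.96, and power = Φ(2.96 − 2.326) = 74%. The same sum gives 55% at 20% mortality and 81% at 50%. The interim looks add the few points seen in column (b).

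**Size with no ceiling, 30–34% mortality.**
- OR 0.75: 17–20% of trials exceed 2000; 95th percentile 2750–2950.
- OR 0.9–1.0: 28–35% exceed 2000; 95th percentile 3350–3550.
- Planned accrual: 800 × 2.5 = 2000 to 1000 × 2.5 = 2500.

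**No trigger by 2000 if it is a ceiling, 30–34% mortality.** About 15–19% of trials at OR 0.75 and 25–33% at OR 0.9–1.0.

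**Could another setting restore 94% at 2000?**
- Looks every 20 patients from 200 give at most 89%, and type I error rises to about 6.6%.
- A 95% threshold gives 86–95%, with type I error of about 12%.
- Normal priors on the log OR with SD 0.5, 1 or 2.5 give 78–80% at 34% mortality.
- Higher ceilings at 30–50% mortality: 2500 gives 86–91%, 3000 gives 90–93%, 4000 gives about 94%.

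**Look schedule.** At the protocol's 70–90 patients a month, three months is 210–270 patients, against 200 in the other statement. At 34% mortality, looks every 50 to 270 patients move power under the ceiling only between 79% and 82%.

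**The case against.** The best defence is that the protocol imposes no ceiling. The synopsis and the Sample Size section both begin with enrolment until a trigger, and both hedge the 2000, one as an expected size and the other as an estimate. Read as fully open-ended, the power and type I error are right, every simulated trial reaches a trigger, and the rule for the final analysis has no gap. All of that stands. It does not make 2000 a maximum, and the sentence giving 94% power refers back to that size.

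A reader might infer three stronger things that the document does not support.
- That the power of this trial is 77–80%. This needs both a ceiling and a control mortality of 30–34%, and the protocol fixes neither.
- That many cohorts will end without a conclusion. This follows only if 2000 is a ceiling.
- That 94% was certainly computed with no ceiling. This is the best fit to the stated figures, but a ceiling near 4000 (2000 per arm) also gives about 94% at 30–50% mortality. The match of the largest average to 2000 is close only near 30% mortality.

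The two look schedules differ in wording but hardly affect power, so they are a minor matter.

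**Conclusion.** The point holds as an incompatibility: under the stated triggers and looks, one of the two figures is wrong whichever way 2000 is read. As a ceiling, it makes the 94% too high by about 8 to 30 points (94 − 86 and 94 − 64), depending on control mortality. As an expected size, it leaves the 94% correct but makes the synopsis's maximum wrong, and the upper tail of sample size goes beyond planned accrual.

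The result rests on a flat prior, a normal approximation, immediate outcome data and no covariate or centre effects. These are not expected to close a gap of this size. The capped power figures depend on a control mortality that the protocol does not state, so they should be quoted as a range.

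**What to change.** State in both the synopsis and the Sample Size section whether 2000 per cohort is a ceiling or an expected size, and give the control mortality used in the simulations.

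- **If it is a ceiling:** restate power at OR 0.75 by control mortality (about 64–86% over 20–50%) and report the chance of reaching 2000 with no trigger. Change the Analyses section so that the final analysis is run at a trigger or at 2000, whichever comes first, and reports the posterior. Cost: a simulation re-run, wording and a less favourable stated power; no extra patients.
- **If it is an expected size:** keep 94%, replace the maximum in the synopsis with the expected size and its 90th and 95th percentiles, and align the accrual statement. The text change is cheap, but it acknowledges that a cohort may need well over 2500 patients.

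In either case, use a single look schedule throughout the Analyses section.

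### The Sample Size section gives a 0% probability of concluding inferiority when OR > 1, which contradicts its own inferiority trigger and matches none of the scenarios it lists

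*Protocol*

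**What the plan says.** Everything at issue is in the protocol's Sample Size section, under Statistical Analyses.

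- Benefit trigger: "A. Superiority ( $\geq 99\%$ posterior probability of $OR < 1$ for 60-day mortality".
- Harm trigger: "B. Inferiority ( $\geq 99\%$ posterior probability of $OR > 1$ for 60-day mortality".
- Equivalence trigger: at least 90% "posterior probability of $0.8 < OR < 1.2$ for 60-day mortality".
- Simulated treatment effects: "OR = 0.75, 0.8, 0.9, 1.0".
- Size: "maximum expected sample size of approximately 2000 patients for each of Early Cohort and Extended Cohort".
- Reported properties, in one sentence: 94% power at OR 0.75, then "0% probability of concluding inferiority when" OR > 1, then a type I error below 5% at OR 1.0.

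The Analyses section adds minimally informative priors, a first interim look once outcomes are available for 750 patients, further looks every 200 patients, and review of the interim results by the DSMB alone.

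**The concern.** Triggers A and B fix the direction of the scale: OR below 1 is benefit and OR above 1 is excess deaths on dexamethasone. A design whose harm trigger fires 0% of the time when OR > 1 would have no working harm boundary. Yet the protocol lists this figure among the design's favourable properties, between power and type I error.

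It is the only statement in the protocol about how the inferiority boundary performs. The trial is open-label, serious adverse events are collected only when judged related to the study drug, and stopping rests on DSMB review of these triggers, so the mortality comparison carries much of the weight in detecting harm. A DSMB member or ethics board reading the sentence is told something false about that boundary. A reader who silently reverses the sign is left with no figure for harm at all.

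**Working it through.** **Step 1: the text against itself.** Trigger B is P(OR > 1 | data) ≥ 0.99. The reported property is P(trigger B fires) = 0% given OR > 1. As the true OR rises above 1 the posterior moves towards OR > 1, so the chance that B fires must rise. The two statements cannot both hold.

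**Step 2: the listed scenarios.** They are 0.75, 0.8, 0.9 and 1.0. The largest is 1.0, so none can yield a probability conditional on OR > 1.

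**Step 3: hand check with a single look at 2000 patients, 1000 per arm.** Assume control mortality of 35%, the middle of the 20-50% range in the protocol's Background section. With a flat prior, B fires when the estimated log OR divided by its standard error exceeds 2.326.

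- Formula: P(B) ≈ Φ(ln OR / SE − 2.326), with SE = √{[1/(p₀(1−p₀)) + 1/(p₁(1−p₁))]/1000}.
- OR 1.25: p₁ = 0.6731/1.6731 = 0.402; SE = √[(4.396 + 4.159)/1000] = 0.0925; ln 1.25 / SE = 0.2231/0.0925 = 2.41; P(B) = Φ(0.09) ≈ 53%.
- OR 0.8: p₁ = 0.4308/1.4308 = 0.301; SE = √[(4.396 + 4.752)/1000] = 0.0956; ln 0.8 / SE = −2.33; P(B) = Φ(−4.66), which is effectively 0%.

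One look already separates the two directions: 0% fits OR 0.8 and does not fit OR 1.25.

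**Step 4: the sequential rule.** The simulation used 40,000 trials per scenario, binomial outcomes, 1:1 allocation, and a normal approximation to the log-OR posterior under a flat prior. All three triggers were active, with looks at 750, 950, …, 1950 and 2000. Control mortality was taken at 20, 30, 35, 40 and 50%.

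| True OR | Inferiority concluded |
|---|---|
| 0.75 | at most 0.01% |
| 0.8 | at most 0.04% |
| 0.9 | 0.2-0.4% |
| 1.0 | about 3% |
| 1.1 | 13-17% |
| 1.25 | 49-66% |
| 1.33 | 71-85% |
| 1.5 | 95-99% |

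Moving the looks to 800, 1000, …, 2000 shifts the ends of the OR 1.25 and 1.33 ranges by about one point (48% at the bottom of the first, 86% at the top of the second). Removing the equivalence stop hardly changes the results: at 35% control mortality and OR 1.25 in the 800-start schedule, 61.7% becomes 62.0%.

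**Step 5: against the protocol's other figures.** Superiority at OR 1.0 is concluded in about 3% of trials, consistent with the stated type I error below 5%. The stated 94% power at OR 0.75 is not reproduced: this unadjusted model gives 63-86%. That limits how far the table can stand in for the sponsor's own results.

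**The case against.** The strongest reply is that this is a slip of one sign. Trigger B is stated correctly, interim inferiority probabilities go to the DSMB, and no stopping decision uses the 0% sentence. That stands, and it limits the point to a mis-stated property. It does not make the sentence harmless, because the error reverses the meaning of the only figure the protocol gives for its harm boundary.

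Four stronger readings are tempting, and the protocol does not support them.

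- **That the trial cannot detect harm.** This follows only from taking the sentence literally. The written rule does detect harm, as the table shows.
- **That the figure is known to belong to OR < 1.** This is a strong inference: the numbers match and only OR ≤ 1 is listed. But the probability of concluding superiority when OR > 1 would also be near zero (0.0-0.5% in the simulation). Only the sponsor's output can settle which was meant.
- **That no harm scenario was simulated.** The protocol lists none. Others may have been run, and the statistical analysis plan is not at hand. The finding is that the protocol states a false figure; leaving fuller operating characteristics to the SAP would be no fault.
- **That the simulated percentages can go into the protocol.** They rest on an assumed baseline risk that the Background does not describe as 60-day mortality. They also omit the planned adjustment for centre, period, sex and oxygen support, and treat an estimated maximum of 2000 as a firm ceiling. A model that misses the stated 94% power should not supply the protocol's figures. Nor does that miss show the 94% to be wrong, since the sponsor's baseline risk and simulation model are not given.

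A misread sign in the extracted text is possible but unlikely, because the signs in triggers A and B read correctly.

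**Conclusion.** The point holds as a wrongly stated operating characteristic. The contradiction with trigger B and the mismatch with the listed scenarios are plain from the Sample Size section and need no assumption. The size of the error does rest on assumptions: control mortality of 20-50%, a flat prior, no covariate adjustment, and a ceiling of 2000. On that basis 0% is wrong by about 49-66 percentage points at OR 1.25 and 71-85 at OR 1.33, at every baseline risk tried. At OR 0.75-0.8 it is right to the stated precision, and at OR 0.9 nearly so, which is why OR < 1 is the likely intended condition. On the same basis, between 34% (100 − 66) and 51% (100 − 49) of trials at OR 1.25 would end without an inferiority conclusion, a property the DSMB would want to know. The design and its triggers need no change on this account; the sentence should be corrected.

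**What to change.** Check the sentence against the sponsor's simulation output and correct the condition, most likely to OR < 1, naming the scenarios it covers. If OR 0.9 is included, quote its value to one decimal place rather than as a bare 0%.

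In place of the false harm figure, give the probability of the inferiority trigger for one or two OR > 1 scenarios, for example 1.25 and 1.33. Take these from the sponsor's own simulation model, and state the baseline mortality and maximum sample size used. The percentages in this note are a plausibility check on that output and should not be copied into the protocol.

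Cost: one corrected sentence and two simulation runs, with no change to the design, the triggers or the sample size.
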